# Reported Outcomes (PROs) assessments:

Patient Reported outcomes should be completed by the trial participants on their own at site, or on their own at home (only applicable when paper versions are used). During the completion of the PROs, the participants should be in a quiet area/room and, as much as possible, with limited interaction (only checking comfort of participants) with the investigator

Page 97 of 177

Proprietary confidential information © 2023 Boehringer Ingelheim International GmbH or one or more of its affiliated companies

or other members of the study team. Questionnaires could be filled within 24 hours prior to scheduled visit for the PRO assessment. There is no specific order for the PROs completion. PROs are listed in Section 2.2. as secondary/further endpoints. Electronic or paper version of PROs and diaries will be implemented based on availability, feasibility, translations, etc.

# 6.1 VISIT SCHEDULE

Study procedures to be performed at each visit are listed in the Flowchart and the respective protocol sections. Please, refer to Section 5 and Appendix 10 for explanations of procedures.

Visits may take place as site visits. However, Visits 7, 9, 15, 20, 22, 24, 26, 28, and 30 could be performed as home visits if acceptable according to local laws and regulations, see Flowchart as reference for procedures to be held during home visits. The type of visit, on-site visit or trial participant's home visit, will be documented in the clinical history and it will be reflected in the eCRFs. The trial procedures conducted/collected during an on-site visit are equivalent to trial procedures conducted at trial participant's home visit. Oversight on the type of visits will be ensured during CQM.

Site staff will agree with the trial participant how they would like to be reminded in advanced about their visits, i.e. phone call prior the scheduled visit or through another procedure agreed with the trial participant.

In those visits requiring safety labs and urine pregnancy test procedures, they should take place prior to the study drug administration. Pre-dose PK/ADA samples will be obtained approximately within 2 hours prior to

Measurements of vital signs should be assessed pre-dose at all dosing visits, and it should precede blood sampling to avoid the impact of it on the vital measurements.

The following sequence of procedures at each visit (where applicable) is recommended: and can be done within each visit window (See Flowchart):

- 1. C-SSRS
- 2. PROs
- 3. Patient diaries (all diaries to be handled/completed by 1st day of the visit)
- 4. AE and concomitant therapy collection; smoking/tobacco/nicotine status
- 5. Physical examinations (including pre-dose vital signs)
- 6. ECG
- 7. Draining fistula count
- 8. Abscess and inflammatory nodule count
- 9. HiSCR, IHS4, HS-PGA, and HASI assessment
- 10. Photographs of skin lesions
- 11. US lesion evaluation (if applicable. See Section 5.4.3)
- 12. Skin biopsies (done guided by US)
- 13. Blood and urine sampling, urine pregnancy testing (if applicable), PK, ADA/NAb, and biomarkers.
- 14. Assign (IRT)/Administer study drug
- 15. Local tolerability
- 16. Post-dose vital signs

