# 4.1.2 Selection of doses in the trial and dose modifications

# Part 1 (Phase IIb)

[figure not shown]
The main trial objectives of Part 1 in this trial is provided in Section 2.1.1.

dosing regimens are defined (for details, see Section 3.1 ) in this trial: one middle dosing regimen (middle dose group)
one higher dosing regimen (high dose group); and one lower dosing regimen (low dose group).
Taken together, trial participants randomised to active treatment in
1368-0052 received then starting Those randomised to placebo in 1368-0052 received placebo until Week 10.
Starting and after final evaluation of Study 1368-0052 (EoT visit), the former placebo trial participants
Thereafter all trial participants were continued
Safety for the lower and medium dosing regimen is supported by the safety profile observed in Study

Page 61 of 177

Proprietary confidential information © 2023 Boehringer Ingelheim International GmbH or one or more of its affiliated companies

In the healthy volunteer (HV) study (1368-0002), 6 healthy volunteers were exposed to the highest 20 mg/kg dose. In those 6 trial participants, no serious adverse event (SAE) or adverse event of special interest (AESI) were reported. At PT level, the most frequently reported treatment-emergent AEs (more than 20% of the trial participants who received spesolimab in the MRD part) were nasopharyngitis, headache, and injection site erythema. All AEs resolved by the end of the trial or were followed up sufficiently. No relevant changes were observed in safety laboratory tests, vital signs, and ECGs. Based on these safety findings from the 1368-0002 study, the highest dose planned for the 1368-0098 study can be considered as acceptable.

Page 62 of 177

Proprietary confidential information © 2023 Boehringer Ingelheim International GmbH or one or more of its affiliated companies

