# 5. ASSESSMENTS

# 5.1 ASSESSMENT OF EFFICACY

The primary, secondary and further endpoints of the study are specified in Section 2.1.2, Section 2.1.3 and Section 2.2.2, respectively.

Efficacy assessments are primarily based on the reduction of HS lesions count evaluated by the investigator (or appropriately qualified delegate). Adequate identification and counting of draining tunnels, abscesses, and inflammatory nodules are key and require careful training. As much as possible, the same or a reduced number of well-trained evaluators should be assessing lesions at one investigative site to reduce unspecific variability as much as possible.

Efficacy will also be assessed in this study according to patient's reporting outcomes including the assessment of skin pain, pruritus, but also drainage and odour, Dermatology Life Quality Index, HiS-QoL.

The description of specific scores, index, or PROs used as efficacy outcome is provided below.

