# 5.2.5.1 Local tolerability

Local tolerability at the administration site of trial medication will be assessed by the investigator during the study drug administration visit and at the time of AE assessment by questioning retrospectively since the last visit. Any observed local tolerability reaction, e.g. "swelling", "induration", "heat", "redness", "pain", and other findings should be reported as an adverse event, see Section 5.2.6.

Suicidal thoughts and behaviour will be assessed by the Columbia-Suicide Severity Rating Scale (C-SSRS) [R08-1147]. The C-SSRS is a semi-structured, investigator-rated interview, developed by clinical experts in cooperation with the FDA, assessing both suicidal behaviour and suicidal ideation. It does not give a global score but provides some categorical and some severity information specifically for behaviour and ideation.

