# Day 1:

- 1. C-SSRS
- 2. PROs
- 3. Patient Diaries (to review from last visit and hand out new diaries to be completed)
- 4. AE and concomitant therapy collection; smoking/tobacco/nicotine status
- 5. Abscess and inflammatory nodule count
- 6. Draining fistula count
- 7. HiSCR, IHS4, HS-PGA, and HASI assessment
- 8. Photographs of skin lesions
- 9. US lesion evaluation (if applicable. See Section 5.4.3)
- 10. Skin biopsies (done guided by US)

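### The recommended visit order puts adverse-event and injection-site questioning ahead of the investigator-judged lesion counts, and nothing separates the interviewer from the counter

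*Protocol*

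**What the plan says.** Protocol Section 6.1 introduces its list of visit procedures with the words "The following sequence of procedures at each visit (where applicable) is recommended". Step 4 is "AE and concomitant therapy collection; smoking/tobacco/nicotine status". Physical examination and ECG follow as steps 5 and 6, "Draining fistula count" is step 7, the AN count is step 8, and HiSCR, IHS4, HS-PGA and HASI are step 9. Dosing is step 14 and local tolerability step 15. The PROs are step 2, so they already precede AE questioning.

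Section 6.2.2 gives a two-day version for visits that are split. There, AE and concomitant-therapy collection is again item 4, and item 5 is "Abscess and inflammatory nodule count". The dT count is item 6 and the scores item 7.

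Section 5.2.5.1 has the investigator assess local tolerability twice: during the dosing visit, and again "at the time of AE assessment by questioning retrospectively since the last visit". A flowchart footnote says the same. Section 5.1 assigns the lesion counts to the investigator or a qualified delegate and stresses training and few evaluators per site. The primary endpoint for Part 1 is the percent change in dT count at Week 8 (SAP Section 5.1).

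Section 4.1.2 reports that in the multiple-dose healthy-volunteer trial the most frequent events, each in more than 20% of spesolimab recipients, "were nasopharyngitis, headache, and injection site erythema".

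**The concern.** The primary endpoint is a count that depends on the evaluator's judgement. Protocol Section 3.2 itself gives control of investigator bias as a reason for the placebo arm. Under the recommended order, the person about to count lesions may first hear about injection-site reactions, infections and changes in therapy since the last visit. If any of that prompts a guess at the treatment, the guess is in the assessor's mind when the primary outcome is recorded. The participants' own ratings are shielded from this by their place in the list; the lesion counts are not.

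The analysis cannot repair this afterwards. The model takes the recorded count as given, and the documents do not describe any recorded treatment guess against which to check it.

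**Working it through.** **Step 1: order and roles, side by side.**

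| Item | Section 6.1 | Section 6.2.2 (two-day version) |
|---|---|---|
| PROs | 2 | 2 (Day 1) |
| AE and concomitant therapy, with retrospective tolerability questions (Section 5.2.5.1) | 4 | 4 (Day 1) |
| Physical examination, ECG | 5, 6 | Day 2 |
| dT count | 7 | 6 (Day 1) |
| AN count | 8 | 5 (Day 1) |
| HiSCR, IHS4, HS-PGA, HASI | 9 | 7 (Day 1) |
| Dosing, then local tolerability | 14, 15 | Day 2 |

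AE questioning comes before the counts in both lists. It is directly adjacent only in the two-day version. The steps that intervene in Section 6.1 do not clear the information, because the targeted examination in Section 5.2.1 includes looking at findings related to adverse events. Sections 5.1 and 5.2.5.1 allow the investigator to do both tasks, and Section 4.1.4.1 on blinding does not separate them.

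**Step 2: could the information point to treatment?** The evidence is limited and mixed.
- For: injection site erythema in more than 20% of spesolimab recipients (Section 4.1.2), and more mild to moderate infections on spesolimab than on placebo (Table 1.4.2: 1).
- Against: no placebo rate is given for the erythema. Section 1.2 describes that trial as intravenous dosing in 40 healthy volunteers, 8 per group at 3:1, with no dose-dependent AEs. The single-dose trial found no relevant difference in AE frequency between groups and no dose dependence.

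**Step 3: scale, by illustration only.** The plan gives no figure to reproduce, and the Part 1 sample size is not visible. Let f be the excess share of active participants whose treatment is guessed from AEs, and b the resulting bias in their percent change. Both are assumptions. The shift in the arm difference is f × b.

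| f | b = 10 | b = 20 | b = 30 |
|---|---|---|---|
| 5% | 0.5 | 1.0 | 1.5 |
| 10% | 1.0 | 2.0 | 3.0 |
| 20% | 2.0 | 4.0 | 6.0 |

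The row f = 20% corresponds to a 20% reaction rate on spesolimab, none on placebo, and a guess after every reaction. Against the assumed maximum effect of 30 points (Section 7.2.3), the range is 0.5/30 = 2% to 6/30 = 20%.

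For one active-versus-placebo contrast at one-sided 0.05, with no true effect, the false-positive rate is Φ(shift / (SD × √(2/n)) − 1.645). The SD of 50 is the value Section 7.5 states for Part 2; n per arm is assumed.
- n = 30, shift 0.5: 50 × √(2/30) = 12.91; 0.5/12.91 = 0.039; rate 0.054.
- n = 50, shift 2 (f = 10%, b = 20): 50 × √(2/50) = 10; 2/10 = 0.20; rate 0.074.
- n = 80, shift 6: 50 × √(2/80) = 7.91; 6/7.91 = 0.76; rate 0.188.

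**Step 4: does the effect need a dose gradient?** No. In SAP Table 7.4: 2 the coefficients sum to zero within rounding, and placebo's is positive in all five models, from 0.458 (exponential) to 0.820 (Emax). A shift of d points favouring all three active arms equally moves each contrast towards rejection by 0.458d to 0.820d.

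**Step 5: what reordering would remove.** Section 3.1 places dosing at Visits 2 to 9, before the Week 8 count at Visit 10. Section 4.1.5 requires monitoring for 2 hours after the first dose and 1 hour after every other dose. Acute reactions at on-site visits are therefore already known. Reordering removes only what is first reported at the visit where the count is made.

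**The case against.** The strongest reply is that the trial is double-blind with matching placebo, the order is only recommended, and no passage requires one person to do both tasks. A reaction that also occurs on placebo says nothing about allocation, and the documents give no placebo rate. Most acute reactions are seen at the dosing visit anyway. Rescue use is a poor clue: it treats HS worsening, which Section 4.2.3 defines by the site's own AN count, and worsening does not identify an arm. All of this stands, and it limits both the likely size of the problem and the gain from a change.

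A second objection bears on the remedy. Section 4.2.3.3 removes lesions treated with a permitted intervention from later counts, so the counter does need one piece of treatment information beforehand. That is correct, and the fix has to carry it. It does not require the rest of the AE interview to come first.

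A reader might infer more than the documents support:
- **That any bias rises with dose and imitates a dose response.** Both trial summaries in Section 1.2 report no dose dependence of AEs.
- **That the plan forces AE questioning immediately before the count.** The order is recommended, and in Section 6.1 two procedures come between.
- **That the blind will in fact be broken.** This is a possibility only; nothing in the documents shows that it will happen.

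**Conclusion.** The point holds as a low-severity design improvement. Both recommended orders put AE, concomitant-therapy and retrospective injection-site questioning before the evaluator-dependent counts, and the interviewer and the counter are not separated. Apart from the treated-lesion rule, the documents give no reason for AE questioning to come first.

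The size of any bias is unknown. The range of 0.5 to 6 points rests on assumed guessing shares and counting shifts, and on an assumed direction favouring active treatment. The false-positive rates also rest on an assumed n, an SD stated for Part 2, and a single contrast in place of the planned multiple-contrast test. These figures show scale and are not evidence that bias will occur. The route is only partly avoidable, because reactions seen at earlier dosing visits remain known.

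**What to change.** In Sections 6.1 and 6.2.2:

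1. Place the dT and AN counts and the HiSCR, IHS4, HS-PGA and HASI assessments directly after the PROs, and ahead of AE, concomitant-therapy and retrospective local-tolerability questioning. All of these stay before dosing.
2. Before the count, give the counter only the list of lesions that have had a protocol-allowed intervention, so that the exclusion in Section 4.2.3.3 can be applied.
3. Where a site already uses a delegate to count, that person should not conduct the AE interview at the same visit.

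The edit can also reconcile the two lists, which disagree on whether dT or AN is counted first and on whether physical examination and ECG come before or after the counts. Section 6 already defers the Part 2 investigational plan to an amendment, which is a natural place to adopt the same order for the confirmatory endpoint.

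The cost is two reordered lists and one extra hand-over item per count, with no added visit, procedure or staff.

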# Clinical Trial Protocol

Page 98 of 177

Proprietary confidential information © 2023 Boehringer Ingelheim International GmbH or one or more of its affiliated companies

In exceptional cases, if standard visits at the trial site are impossible, because of COVID-19 related safety risks, the investigator must assess the risk-benefit for each individual patient and may decide to perform a visit remotely if this is in the best interests of the trial participants and if agreed with the sponsor.

All COVID-19 related deviations from the original schedule of visits and procedures will be documented and the implications considered for the analysis of the trial data.

All deviations from the original schedule of visits and procedures will be documented and the implications considered for the analysis of the trial data.

# 6.2 DETAILS OF TRIAL PROCEDURES AT SELECTED VISITS

In the event of force majeure or other disrupting circumstances remote visits may have to be performed as follows: by video call or phone, whatever is available and feasible for each trial participant. Video call is the preferred option as C-SSRS interview benefits from body language and eye contact information that can be missed by phone.

If a participant is not able or willing to come to the site for a trial visit, remote visits (by video call or phone) should be performed instead. The following assessment can be done remotely:

- Collection of adverse events from last visit
- Any change in concomitant therapies from last visit
- C-SSRS

NRS for pain and pruritus, DLQI, HiS-QoL, FACIT-Fatigue scale, Patient Global Impression of Change (PGI-C), Patient Global Impression of Severity (PGI-S), HADS, HODS. — Those questionnaires will be available in paper or electronic format. These questionnaires should be answered by the participant. Participants will be supplied with the questionnaires to be filled out at home. The questionnaires should be answered on the day of the remote visit or within the visit window range and sent back to the site thereafter.

# **Home Healthcare Nurse**

Only for visits where a Home Healthcare Nurse is an option, the following assessments can be done at the participant's home, when applicable according to the Flowchart:

- C-SSRS
- Physical examination
- Vital signs
- Administration of study medication
- NRS Pain and NRS pruritus: Review completed Patient's Diary in case paper version is used. Or oral check completed when electronic version is used
- Review paper HS pain medication diary
- AEs collection
- Concomitant therapy review

Clinical Trial Protocol

Page 99 of 177

Proprietary confidential information © 2023 Boehringer Ingelheim International GmbH or one or more of its affiliated companies

And remind the trial participant about the date for the next study visit.

The study medication will be sent from site to the patient's home by courier. The nurse performing the home visit should check that the medication is fit for use. After the visit is completed, the nurse should send to site the documentation from the visit. The used and unused medication will be returned to site by the courier vendor (within 72 hours after the visit) for accountability purposes and destruction.

# Safety lab, as per Flowchart

If blood sampling for central lab at the trial site is not possible, in exceptional cases (e.g., due to COVID-19 pandemic, travel restrictions, central lab kit stock out issues, etc.), the safety lab analyses can be performed at a local lab until central lab testing becomes available. The results of the local lab tests must be transferred to the investigator to ensure medical review and proper documentation of the lab results with clinical relevance for safety on the clinical records and in the eCRFs as AEs.

Under these exceptional circumstances, standard collection of lab values, must be included in eCRFs by site staff as accreditation/reference ranges are required.

# 6.2.1 Screening period

# **Screening Period**

Study requirements, including the procedure for the follow-up of prematurely withdrawn patients must be fully explained to the trial participant and written informed consent obtained prior to initiating any study-related evaluation. The importance of staying in the trial until completion of all study requirements will be emphasized. No trial procedures should be done unless the patient has consented to taking part in the trial.

Once consented, the patient is considered to be enrolled in the trial and has started screening. The trial participant should be recorded on the enrolment log and be registered in as a screened patient. Trial participants will be assigned a patient number generated via the system.

Screening (Visit 1) should normally take place no more than 28 days before Visit 2. Visit 1 procedures may be completed over multiple physical visits, if needed. The time window for Visit 1 may be extended at the discretion of the CT Manager in conjunction with the CT Leader on a case by case basis.

For the comprehensive list of the trial procedures required at the Screening Visit (Visit 1) please refer to Flowchart. Trial participants who have a laboratory test value that makes their participation uncertain may have the test repeated to determine eligibility; however, the result must be available prior to Visit 2 (Day 1). Baseline conditions and medical history will be assessed during screening.

During the screening visit, the following demographics information will be collected:

- Age on the day of informed consent (in years)
- Sex (male, female in order to describe the trial participant's sex at birth)
- Gender identity (male, female, non-binary, not answered, or other in order to describe how the trial participant self-identifies, regardless of their genotypic or phenotypic

# c40061625-02 Clinical Trial Protocol Page 100 of 177

Proprietary confidential information © 2023 Boehringer Ingelheim International GmbH or one or more of its affiliated companies

sex) if 1) locally accepted (i.e. based on HA/EC/IRB acceptance, independent of acceptance by investigators or participants), 2) investigators are willing to ask, and 3) participants are willing to reply

- For women of childbearing potential, yes/no in order to characterise the patient population and as a basis for contraception requirements
- Ethnicity and race in order to sufficiently characterise the patient population, to support possible subgroup analyses

# **Baseline Conditions**

Chronic diseases, current observable conditions, any new clinically relevant findings discovered from the physical examination, ECG, safety labs, and any condition requiring therapy will be reported on the Baseline Condition eCRF page. The smoking status and history based on the calculation of pack-years will be collected as well.

# Infection screening

Infection testing will include tuberculosis, hepatitis B, hepatitis C, and HIV assessments (see Section 3.3.3 and Table 5.2.3: 2).

# Medical History

Medical history of HS, including the previous treatment, will be collected and reported in the eCRF.

Information on clinically significant previous and concomitant illnesses, other than HS, or any clinically significant signs or symptoms that are present before informed consent, or pre-existing conditions identified through findings from assessments and examinations done during the screening visits will be recorded as medical and surgical history at screening on the Baseline Condition page in the eCRF.

# Fitzpatrick skin type

Assessment on the type of skin should be done using the Fitzpatrick skin type scale, see Appendix 10.22 for reference.

Patients who fail screening (i.e. does not meet the eligibility criteria) following Visit 1 assessments should be registered as a screen failure in

